6. STUDY PROCEDURES

6.1 Schedule of Evaluations

Randomized Control Trial

Treatment Variables. Main patient reported treatment outcomes (PROs) include pain intensity and anxiety. The use of self-reported pain ratings to assess pain is standard clinical practice.^{68,69} Although self-report of pain intensity is subjective, a reliable physiological measure to quantify pain has not been identified.⁷⁰ These measures will be collected via tablet computer in the PHI-approved data collection tool (REDCap). A similar process was used in [name]'s pilot RCT. The study staff will hand the patient a tablet for confidential self-administration. Once the patient completes the questionnaires, the answers will be masked so the research staff will not have access to the scores. To keep research staff blinded to scores, the data collection tool will be designed so that the study staff will only be able to determine that valid pain and anxiety scores were entered by the patient. In other words, staff will not have access to the actual pain or anxiety scores until the statistician conducts the final analysis. Data will be collected as shown in Table below.

Treatment Variables	Measure/Source	Data Collection Time point			
		Pre-Treatment	Post-Treatment	ED Discharge	1-week and 4-week Follow-up
Primary Assessment (* and bold)					
Pain Intensity	Numeric Rating Scale, 0-10^{58,59}	X	X*	X*	X^
Anxiety	Numeric Rating Scale, 0-10^{58,59}	X	X*	X*	X^
Secondary Assessment (^ and italic)					
All pain medications in the ED	EHR			X^	
Pain medication/opioid use	Self-report				X^
Baseline variables of interest					
Demographics	EHR data and self-report	X			
Current Medications		X			
Opioid use – last 30 days	Self-report	X			
Previous acupuncture use		X			

ED visits in last year	X
Other variables of interest	
Expectancy	Self-report
Satisfaction questions	X
ED impact (ACUPUNCTURE ONLY)	X

Qualitative Interviews

Patient Interview Guide

U01 Acupuncture Study Patient Interview Topic Guide Preliminary Draft 10-23-20
1. Pain narrative—history, cause, impact, course, treatment experiences Possible prompts: i. Tell me about your pain condition... ii. How long have you had it? iii. What causes it? iv. How does it impact you? v. Tell me about your pain condition over time—wax/wane? Always the same? Exacerbating issues? vi. Tell me about your treatment and management experiences

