INSTRUCTIONS: I will now be asking you some questions about you as well as some questions about your health.

- 1. What area of your body is experiencing the most pain at the present moment?
 - a. Abdomen
 - b. Headache- not migraine
 - c. Flank
 - d. Chest- non-emergent
 - e. Back
 - f. Limb
 - g. Groin
 - h. OTHER [FREE TEXT]
- 2. Has your pain that lasted 4 months or longer? (Radio)
 - a. Yes
 - b. No

- c. Do not know
- d. Decline to answer

3. Are you currently taking any pain medications (Radio)?

- a. Yes
- b. No
- c. Do not know
- d. Decline to answer

i. If yes, please identify any pain medication(s) you are taking. Please select all that apply. (radio):

- 1. Oxycodone (OxyContin, Oxecta, Roxicodone)
- 2. Oxycodone / Acetaminophen (Percocet, Endocet, Roxicet)
- 3. Oxycodone and Naloxone (Targiniq ER)
- 4. Fentanyl (Actiq, Duragesic, Fentora)
- 5. Methadone (Dolophine, Methadose)
- 6. Morphine (Astramorph, Avinza, Kadian, MS Contin, Ora-Morth SR)
- 7. Codeine
- 8. Tylenol with codeine
- 9. Hydrocodone (Hysingla ER, Zohydro ER)
- 10. Hydrocodone / Acetaminophen (Lorcet, Lortab, Norco, Vicodin)
- 11. Hydromorphone (Dilaudid, Exalgo)
- 12. Aspirin
- 13. Tylenol
- 14. Ibuprofen
- 15. Naproxen
- 16. Celebrex
- 17. Other: [FREE TEXT]
- 18. Do not know
- 19. Decline to answer

ii. IF yes, how often have you taken prescription pain medications?

- 1. Several times a day
- 2. Once a day
- 3. Several times a week
- 4. Once a week
- 5. Several times per month
- 6. Once per month
- 7. Can't recall
- 8. Decline to answer
- 9. Other: [FREE TEXT]

4. Have you taken any pain medications within the last 30 days?

- a. Yes

- b. No
- c. Do not know
- d. Decline to answer
 - i. If yes, please identify the opioid(s). Please select all that apply:
 - 1. Oxycodone (OxyContin, Oxecta, Roxicodone)
 - 2. Oxycodone / Acetaminophen (Percocet, Endocet, Roxicet)
 - 3. Oxycodone and Naloxone (Targiniq ER)
 - 4. Fentanyl (Actiq, Duragesic, Fentora)
 - 5. Methadone (Dolophine, Methadose)
 - 6. Morphine (Astramorph, Avinza, Kadian, MS Contin, Ora-Morth SR)
 - 7. Codeine
 - 8. Tylenol with codeine
 - 9. Hydrocodone (Hysingla ER, Zohydro ER)
 - 10. Hydrocodone / Acetaminophen (Lorcet, Lortab, Norco, Vicodin)
 - 11. Hydromorphone (Dilaudid, Exalgo)
 - 12. Aspirin
 - 13. Tylenol
 - 14. Ibuprofen
 - 15. Naproxen
 - 16. Celebrex
 - 17. Other: [FREE TEXT]
 - 18. Do not know
 - 19. Decline to answer
 - ii. If yes, how often were you taking prescription pain medications?

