 - 1. Several times a day
 - 2. Once a day
 - 3. Several times a week
 - 4. Once a week
 - 5. Several times per month
 - 6. Once per month
 - 7. Can't recall
 - 8. Decline to answer
 - 9. Other: [FREE TEXT]

5. Have you visited an emergency room for pain within the past 12 months?

- a. Yes
- b. No
- c. Do not know
- d. Decline to answer
 - i. If yes, how many times in the last year?
 - 1. 1

- 2. 2-4
- 3. 5-7
- 4. 11+
- 5. Decline to answer

6. Have you used any non-medication treatments for your pain?

- a. Yes
- b. No
- c. Don't know
- d. Decline to answer
 - i. If yes, what methods have you used? Please select all that apply.
 - 1. Physical Therapy
 - 2. Chiropractor
 - 3. Massage
 - 4. Exercise
 - 5. Acupuncture
 - 6. Hot / cold therapy
 - 7. Meditation
 - 8. Decline to answer
 - 9. OTHER [FREE TEXT]

7. Have you ever received acupuncture?

- a. Yes
- b. No
- c. I don't know
 - i. If yes, was the acupuncture effective to relieve your symptoms?
 - 1. Yes
 - 2. No
 - 3. Do not know
 - 4. Decline to answer

8. Please rate your confidence that non-medication treatments can reduce pain, on a 0-10 scale, where 0 is not confident and 10 is completely confident.

0 1 2 3 4 5 6 7 8 9 10 Unsure

“PRE” FORM – Patient facing, same for both arms, blinded to coordinator

INSTRUCTIONS: “There are some additional questions for you to answer on this iPad or your phone. I will be here to answer any questions you may have. Please do not show me the answers to these questions. Please hand the iPad back to me when you are done or let me know when you have completed the survey on your phone.”

SECTION 1 – Demographics Patient Facing, to be answered by the patient; blinded. Questions need to be presented as shown here in longitudinal fashion.

1. What is your date of birth?
2. What is your ethnicity?
 - a. Hispanic or Latinx
 - b. Not Hispanic or Latinx
 - c. Decline to answer
3. What is your race? Check all that apply.
 - a. American Indian or Alaska Native
 - b. Asian
 - c. Black or African American
 - d. Native Hawaiian or other Pacific Islander
 - e. White
 - f. Other [FREE TEXT]
 - g. Decline to answer
4. My sex assigned at birth is:
 - a. Female
 - b. Male
 - c. Intersex
 - d. Decline to answer
5. What is your current gender identity?
 - a. Male
 - b. Female
 - c. Trans male/Trans man
 - d. Trans female/Trans woman
 - e. Genderqueer/Gender non-conforming
 - f. Different Identity [FREE TEXT]
 - g. Decline to answer
6. How much formal education do you have?

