2. Please rate your anxiety, **right now**, on a scale of 0 to 10, where 0 is no anxiety, and 10 is the worst anxiety imaginable.

0 1 2 3 4 5 6 7 8 9 10

SECTION 3 – Satisfaction

3. How satisfied are you with how your pain was managed during your ED visit?

- a. Very Unsatisfied
- b. Somewhat Unsatisfied
- c. Neutral
- d. Somewhat Satisfied
- e. Very Satisfied

4. Overall how satisfied are you with your treatment during your ED visit?

- a. Very Unsatisfied
- b. Somewhat Unsatisfied
- c. Neutral
- d. Somewhat Satisfied
- e. Very Satisfied

FOLLOW UP FORM for 1 week F/U AND 4 week F/U – To be completed by everyone, ideally from an automatic text and email generated by REDCap. If not by email, coordinator will text or phone the participant and enter the answers into REDCap.

Instructions: Below are some questions that ask you to remember what happened since your discharge from the Emergency Room on [er_visit_date].

Section 1-Medications

1. Since your discharge from the Emergency Room on [er_visit_date], have you taken any pain medications for your medical condition?
 - a. Yes
 - b. No
 - c. I don't know
 - i. If yes, “were these medications prescribed by a medical professional?

Check all that apply:

1. Yes, by Emergency room provider

2. Yes, by Primary Care Provider
 3. Yes, by Other medical professional [FREE TEXT]
 4. No
 5. I don't know
2. [branched from 1.a.i.1] Since your discharge, which pain medication(s) was prescribed by your EMERGENCY ROOM PROVIDER? Please select all that apply. (radio):
 1. Oxycodone (OxyContin, Oxecta, Roxicodone)
 2. Oxycodone / Acetaminophen (Percocet, Endocet, Roxicet)
 3. Oxycodone and Naloxone (Targiniq ER)
 4. Fentanyl (Actiq, Duragesic, Fentora)
 5. Methadone (Dolophine, Methadose)
 6. Morphine (Astramorph, Avinza, Kadian, MS Contin, Ora-Morth SR)
 7. Codeine
 8. Tylenol with codeine
 9. Hydrocodone (Hysingla ER, Zohydro ER)
 10. Hydrocodone / Acetaminophen (Lorcet, Lortab, Norco, Vicodin)
 11. Hydromorphone (Dilaudid, Exalgo)
 12. Aspirin
 13. Tylenol
 14. Ibuprofen
 15. Naproxen
 16. Celebrex
 17. Other: [FREE TEXT]
 18. Do not know
 19. Decline to answer
- a. How often have you taken these pain medication(s) on average?
 1. Several times a day
 2. Once a day
 3. Several times a week
 4. Once a week
 5. Several times per month
 6. Once per month
 7. Can't recall
 8. Decline to answer
 9. Other: [FREE TEXT]

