3. [branched from 1.a.i.2] Since your discharge, which pain medication(s) was prescribed by your PRIMARY CARE PROVIDER? Please select all that apply. (radio):
 1. Oxycodone (OxyContin, Oxecta, Roxicodone)
 2. Oxycodone / Acetaminophen (Percocet, Endocet, Roxicet)
 3. Oxycodone and Naloxone (Targiniq ER)

4. Fentanyl (Actiq, Duragesic, Fentora)
5. Methadone (Dolophine, Methadose)
6. Morphine (Astramorph, Avinza, Kadian, MS Contin, Ora-Morth SR)
7. Codeine
8. Tylenol with codeine
9. Hydrocodone (Hysingla ER, Zohydro ER)
10. Hydrocodone / Acetaminophen (Lorcet, Lortab, Norco, Vicodin)
11. Hydromorphone (Dilaudid, Exalgo)
12. Aspirin
13. Tylenol
14. Ibuprofen
15. Naproxen
16. Celebrex
17. Other: [FREE TEXT]
18. Do not know
19. Decline to answer

- a. How often have you taken these pain medication(s) on average?
 1. Several times a day
 2. Once a day
 3. Several times a week
 4. Once a week
 5. Several times per month
 6. Once per month
 7. Can't recall
 8. Decline to answer
 9. Other: [FREE TEXT]
4. [branched from 1.a.i.3] Since your discharge, which pain medication(s) was prescribed by ANOTHER MEDICAL PROFESSIONAL? Please select all that apply. (radio)
 1. Oxycodone (OxyContin, Oxecta, Roxicodone)
 2. Oxycodone / Acetaminophen (Percocet, Endocet, Roxicet)
 3. Oxycodone and Naloxone (Targiniq ER)
 4. Fentanyl (Actiq, Duragesic, Fentora)
 5. Methadone (Dolophine, Methadose)
 6. Morphine (Astramorph, Avinza, Kadian, MS Contin, Ora-Morth SR)
 7. Codeine
 8. Tylenol with codeine
 9. Hydrocodone (Hysingla ER, Zohydro ER)
 10. Hydrocodone / Acetaminophen (Lorcet, Lortab, Norco, Vicodin)
 11. Hydromorphone (Dilaudid, Exalgo)

12. Aspirin
13. Tylenol
14. Ibuprofen
15. Naproxen
16. Celebrex
17. Other: [FREE TEXT]
18. Do not know
19. Decline to answer

a. How often have you taken these pain medication(s) on average?

1. Several times a day
2. Once a day
3. Several times a week
4. Once a week
5. Several times per month
6. Once per month
7. Can't recall
8. Decline to answer
9. Other: [FREE TEXT]

5. [branched from 1.a.i.4] Since your discharge from the emergency room on [er_visit_date], which pain medication(s) have you taken (not prescribed by your emergency room provider, primary care provider or other medical professional)? Please select all that apply

1. Oxycodone (OxyContin, Oxecta, Roxicodone)
2. Oxycodone / Acetaminophen (Percocet, Endocet, Roxicet)
3. Oxycodone and Naloxone (Targiniq ER)
4. Fentanyl (Actiq, Duragesic, Fentora)
5. Methadone (Dolophine, Methadose)

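### Follow-up items 2 to 4 and baseline item 3 pair a select-all instruction with a radio field, and each prescriber block pools opioid and non-opioid frequency, so opioid use could be missed or its frequency not isolated.

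*Combined protocol and SAP*

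**What the plan says.** Section 6.1 (Schedule of Evaluations) lists "Pain medication/opioid use" by self-report at 1 and 4 weeks as a secondary assessment. The instrument is the Follow Up Form in Appendix B, Section 1. A gate question asks who prescribed the drugs and accepts several answers, so up to four source blocks can open: emergency provider (item 2), primary care (item 3), another professional (item 4) and not prescribed (item 5).

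Item 2 ends with the instruction and tag "Please select all that apply. (radio". Item 3 does the same: "which pain medication(s) was prescribed by your PRIMARY CARE PROVIDER? Please select all that apply. (radio". So does item 4: "ANOTHER MEDICAL PROFESSIONAL? Please select all that apply. (radio". Item 5 has the select-all instruction without the tag. Each list mixes opioids (options 1 to 11) with aspirin, Tylenol, ibuprofen, naproxen and Celebrex (options 12 to 16). Each block then has one frequency item: "How often have you taken these pain medication(s) on average".

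On the Baseline Form, item 3 has the same conflict: "please identify any pain medication(s) you are taking. Please select all that apply. (radio". Baseline item 5 asks "If yes, how many times in the last year" and offers 1, 2-4, 5-7, 11+ or declining to answer.

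**The concern.** A radio field holds one answer. The build specification therefore contradicts the question put to the patient, and the programmer has to choose between them. One choice can drop a drug that the patient would have reported. The other keeps every drug but leaves one frequency to cover opioids and non-opioids together.

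This matters because Section 2.1 names the absence of follow-up opioid data as a gap in earlier trials and says that this study will fill the listed gaps. The form is meant to be completed mainly by the patient from an automatic text or email, so usually no interviewer is present to notice a problem. Nor would the completeness checks in Section 9.5.1 reveal it, because a radio field with one answer counts as complete. The trial exists to refine procedures for a larger RCT, so a faulty instrument could be carried forward.

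**Working it through.** No figure in the plan depends on this point, so there is none to reproduce. The check sets the items side by side.

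| Item (Appendix B) | Select-all instruction | Radio tag | Frequency item |
|---|---|---|---|
| Follow-up 2, emergency provider | yes | yes | one, for the block |
| Follow-up 3, primary care | yes | yes | one, for the block |
| Follow-up 4, other professional | yes | yes | one, for the block |
| Follow-up 5, not prescribed | yes | no | one, for the block |
| Baseline 3, current drugs | yes | yes | one, for prescription drugs |
| Baseline 4, last 30 days | yes | no | one, for prescription drugs |

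**Does the tag mean single choice?** The Screening Form instruction assigns radio buttons to Yes/No responses, and the stems of baseline items 2 and 3 use the tag for single-answer questions. Other multi-answer items (race, baseline items 4 and 6, follow-up items 5 and 9) do not carry it. The natural reading is a single-answer field, which conflicts with the instruction beside it in four items.

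**Radio build.** Each of follow-up items 2 to 4 stores one drug. Let c be the share of opioid users who also report a separately listed non-opioid from the same source and report no opioid in another block. Let q be the probability that such a patient keeps the opioid as the one answer. Then

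share of opioid users recorded = 1 - c x (1 - q).

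The documents give neither c nor q. On assumed values:

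| c | q = 0 | q = 0.5 | q = 1 |
|---|---|---|---|
| 0.25 | 75% | 87.5% | 100% |
| 0.50 | 50% | 75% | 100% |
| 0.75 | 25% | 62.5% | 100% |

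For example, 1 - 0.50 x (1 - 0.5) = 0.75. Over this grid the loss runs from 0% to 75%, which shows only that the size cannot be fixed from the documents.

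**Checkbox build.** Every ticked drug is stored, so this loss is zero. But items 2 to 4 ask which drugs were prescribed, and the only measure of how much was taken is the block's single frequency item. When an opioid and a non-opioid are ticked in one block, the answer belongs to neither. The resulting error in opioid frequency can go in either direction.

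**ED visits.** The options 5-7 and 11+ leave 8, 9 and 10 without an answer.

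**The case against.** The strongest reply is that the tag may be a stray note to the programmer. The patient-facing words ask for several answers, parallel lists have no tag, and the documents do not show the REDCap fields as built. That stands. A reader might infer that opioid use will be under-recorded, but the documents support only that it could be.

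A reader might also infer that one frequency covers all drugs, or that opioid use cannot be told apart from self-bought medicines. The form does not support either. Frequency is asked once per source block, up to four times, and non-prescribed drugs go to item 5 with its own frequency. Pooling arises only within a source.

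Several features limit the harm. Oxycodone/acetaminophen, hydrocodone/acetaminophen and Tylenol with codeine are single options, so these combinations survive a radio build. Baseline item 4 gives a second, untagged record of opioids at entry. The EHR extract in Section 10.2 includes opioid prescriptions at discharge, which cross-checks emergency prescribing, but it does not show use after discharge or other prescribers. Lost drugs and pooled frequency mostly arise under different builds and should not be added together.

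Finally, Sections 9.5 and 9.6 set out no analysis of opioid frequency, and the primary outcomes are recruitment and retention. This lowers the stakes but does not remove the contradiction. Monthly frequency options at 1 week (at most 7 + 4 = 11 days after discharge) come from sharing one form between visits and are a minor point.

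**Conclusion.** The point holds in a conditional form. Three of the four follow-up drug lists, and baseline item 3, contradict themselves on field type. Under a radio build, opioid use could be missed in patients who report an opioid and a non-opioid from the same prescriber. Under a checkbox build, opioid frequency cannot be isolated for those patients. Neither build gives a clean record for them.

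The size is unknown. It depends on how the fields were built, on how many patients receive both kinds of drug from one source and, for a radio build, on which answer they keep. The grid above is an illustration on assumed inputs and not an estimate. The missing 8-10 category is a separate small defect in a baseline descriptor.

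The effect is confined to a listed secondary assessment and to baseline description; recruitment, retention and the pain scores are untouched. Correction is still worthwhile, because the trial is meant to test data collection and the EHR does not replace the self-report.

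**What to change.** - Specify checkbox fields for baseline item 3 and for follow-up items 2, 3 and 4, and remove the radio tag from those lists.
- Within each source block, ask frequency once for opioids and once for non-opioids, each shown only if a drug of that kind is ticked. Keep the split by source.
- Make the ED-visit options 1, 2-4, 5-7, 8-10 and 11+.
- If data have already been collected, state which field type was in use and from when, so that the analysis can say which limitation applies.

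The cost is a change of field type, a few added items and a slightly longer form for patients who report both kinds of drug.

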9. OTHER [FREE TEXT]

10. (Acupuncture Arm Only) Since your discharge from the Emergency Room on [er_visit_date], have you received acupuncture?

- a. Yes
- b. No
- c. Do not know

i. If yes, was the acupuncture effective to relieve your symptoms?

1. Yes
2. No
3. Do not know

11. Since your discharge from the Emergency Room on [er_visit_date], have you experienced new or worsening ILLNESS?

- a. No

b. Yes

IF YES PLEASE DESCRIBE [FREE TEXT]

12. Since your discharge from the Emergency Room on [er_visit_date], have you experienced new or worsening PAIN?

- a. No
- b. Yes
- c. Don't know

IF YES PLEASE DESCRIBE [FREE TEXT]

13. Since your discharge from the Emergency Room on [er_visit_date], have you experienced new or worsening HEALTH ISSUES?

- a. No
- b. Yes
- c. Don't know

IF YES PLEASE DESCRIBE [FREE TEXT]

Instructions: Below are some questions that ask you to rate how you are feeling right now.

SECTION 2 – Pain

1. Please rate your pain, right now, on a scale of 0 to 10, where 0 is no pain, and 10 is the worst pain imaginable.

0 1 2 3 4 5 6 7 8 9 10

SECTION 3 – Anxiety

2. Please rate your anxiety, right now, on a scale of 0 to 10, where 0 is no anxiety, and 10 is the worst anxiety imaginable.

0 1 2 3 4 5 6 7 8 9 10

SECTION 4 – Satisfaction

3. “How satisfied were you with how your pain was managed during your ER visit” on the 5-point Likert scale.

- a. Very Unsatisfied
- b. Somewhat Unsatisfied
- c. Neutral
- d. Somewhat Satisfied
- e. Very Satisfied

4. "Overall how satisfied were you with your treatment during your ER visit?" on the same Likert Scale.
 - a. Very Unsatisfied
 - b. Somewhat Unsatisfied
 - c. Neutral
 - d. Somewhat Satisfied
 - e. Very Satisfied

FOLLOW UP FORM for 1 week F/U (Acupuncture Arm Only, if Post Acupuncture Form Ear Seeds question is "Yes")

SECTION 5 – Ear Seeds

1. Before this follow-up, did you remove the ear seeds that you received in the ER on [er_visit_date]
 - a. Yes
 - i. If yes, when did you remove them? [enter date]
 - b. No (if no, you should remove them now)
2. After your ER discharge, did you ever stimulate/touch the ear seeds yourself for pain relief?
 - a. Yes
 - b. No
3. Any comments on the ear seeds [FREE TEXT]

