Results: During the study period, the acupuncturist was referred and then approached 24 patients. Informed consent was obtained from 79% (19/24) of patients. The average pain pre-treatment score was 4.68, and the post-treatment change was a decrease of -2.07 units and ED discharge change was a reduction of -1.68 units. Ear seeds were used in a majority (14/19) of patients. Phone calls were only successful in 8 patients due to the holidays. Seven of eight patients reported retaining the ear seeds in place until the 1-week follow-up. The 1-week pain reduction was of -3.68 units.

“Lessons learned”: (1) extended auricular therapy (ear seeds) was well tolerated by patients; and (2) ear seeds may provide pain relief at 1-week.

Rationale for the Proposed Study: Despite these positive findings in the pilot RCT and two observational studies, there are several issues that need to be addressed before proceeding to a future definitive study. First, a better understanding of process outcomes such as recruitment/reach, stakeholder acceptability, and intervention fidelity are needed to ensure optimal recruitment and minimal patient attrition. We will assess these outcomes carefully in this study. We are also introducing several improvements at the outset. For example, to improve retention, we will reduce the follow up period to 1-week and use text messaging features of REDCap. To improve fidelity, we will develop a ‘responsive’ manualized-based intervention (consensus protocol with options) and a corresponding fidelity assessment tool. Finally, intervention observations and interviews with stakeholders (ED providers and administrators, ED

patients and study acupuncturists) will provide valuable explanatory data regarding barriers and facilitators to implementation that will be useful for a future, multi-site, pragmatic, definitive RCT. **Taken together, our understanding of the current gaps in the literature, promising results from our observational studies, and our operational knowledge gained from the pilot RCT combine to provide the necessary evidence and expertise to support the conduct of the proposed, multi-site feasibility clinical trial.**

Aim 1: Develop a Manualized Acupuncture Intervention

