- The acupuncture therapy intervention will be based on staging an interview/conversation, palpation, and selection of points or methods for treatment based on presenting factors. The acupuncturist will record the specific acupuncture points, the number of needles used, length of needle retention if applicable, length of session time, any limitations on session time, points used for extended auricular therapy, if applicable, and response from point stimulation based on parameters of the responsive manualization protocol (Aim 1). A consensus of common points utilized for acute pain in the ED can be expected with additional points at the discretion of the acupuncturist treating the patient. Hand rotation and perturbation of needles to de qi status is allowed; electrical stimulation or moxibustion are not included in this trial. Needle retention time can vary and may range from 5-40 minutes, but commonly will be 15-30 minutes. Total session time may vary due to the patients' tolerance of the treatment, acupuncturists' assessment of the patient or workflow consideration of the ED, such as a patient needing to leave the room for imaging to be performed.
- Sterile, single-use non-coated acupuncture needles will be used for this study. Needles in sizes of .22x13mm, .25x25mm, .25x40mm, and .30x40mm, and will be available. The choice of needle size used will be left to the discretion of the acupuncturists treating the patient.
- Treatment regimen: Each patient randomized to the Acupuncture arm will be provided no more than one treatment per admission to the ED. Due to workflow considerations of the ED of this pragmatic RCT, it is possible that some patients randomized to the Acupuncture arm of the study will not receive acupuncture.
- Extended therapy pressure: Ear seeds will be retained on auricular acupuncture points in order to "extend the treatment benefit after ED care". We will use vaccaria seed with latex adhesive, and have a non-latex alternative for patients with latex allergy. Use and location of the ear seeds will be at the discretion of the acupuncturist. Patients will keep them on the ears after discharge from the ED, and are directed to leave them on until they fall off or remove them if they become uncomfortable. The ear seeds can be peeled off and thrown into the trash

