1 week follow-up Assessment (Follow-up) will be obtained via REDCap based text message or email (or phone call from research staff) at 1 week (+/- 4 days) of patient's ED discharge for both arms. To maintain assessor blinding, any 1-week phone calls (if needed) will be conducted by a research staff (SC or RA) who did not interact with the patient during their study participation in the ED.

- Pain Assessment (Post) using a 0-10 NRS
- Anxiety scores using a 0-10 NRS
- Satisfaction and will be measured through brief questions. All participants will be asked to answer;
 - “How satisfied are you with how your pain was managed during your ED visit” on the 5-point Likert scale.
 - “Overall how satisfied are you with your treatment during your ED visit?” on the same Likert Scale.
- Pain medications utilized from ED discharge to 1 week after discharge will be obtained from patients via phone call, email, or text messaging via the secure REDCap electronic data collection tool.

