6.2.5 Completion/Final Evaluation

Four Week Follow-Up Assessment Visit

4 week follow-up Assessment (Follow-up) will be obtained via REDCap based text message or email (or phone call from research staff) at 4 week (+/- 4 days) of patient's ED discharge for both arms. To maintain assessor blinding, any 4-week phone calls (if needed) will be conducted by a research staff (SC or RA) who did not interact with the patient during their study participation in the ED.

- Pain Assessment (Post) using a 0-10 NRS
- Anxiety scores using a 0-10 NRS
- Satisfaction and will be measured through brief questions. All participants will be asked to

answer:

- "How satisfied are you with how your pain was managed during your ED visit" on the 5-point Likert scale.
- "Overall how satisfied are you with your treatment during your ED visit?" on the same Likert Scale.
- Pain medications utilized from ED Discharge to 4 weeks after discharge will be obtained from patients via phone call, email, or text messaging via the secure REDCap electronic data collection tool.

Early Termination

The study doctor or the sponsor can stop a subject's participation at any time without their consent for the following reasons:

- If it appears to be medically harmful to them;
- If they fail to follow directions for participating in the study;
- If it is discovered that they do not meet the study requirements;
- If the study is canceled; or
- For administrative reasons, including competitive enrollment (e.g. the target number of subjects has entered the study.)
- If the patient's clinical condition worsens emergently as determined by the ED physician/clinician.

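### The protocol text sets no end date for ear-seed wear, but the 1-week form tells patients who have not removed the seeds to take them out, and it has no answer for seeds that fell off

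*Combined protocol and SAP*

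**What the plan says.** Section 3 (description of the intervention) and Section 5.1 carry the same direction. After discharge, patients keep the seeds on and "are directed to leave them on until they fall off or remove them if they become uncomfortable". Neither section gives a time limit, and Section 5.2 gives no wear time. Both sections present the seeds as the component meant to prolong the benefit after the ED visit, and leave their use and location to the acupuncturist. Section 5.1 adds that each acupuncture patient receives an after-care sheet covering the seeds; its text is not in the documents.

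The 1-week follow-up form in Appendix B has an ear-seed section shown under this condition: "Acupuncture Arm Only, if Post Acupuncture Form Ear Seeds question is" answered yes. It asks whether the patient removed the seeds before this follow-up. A positive answer opens a date field. The negative answer reads: "No (if no, you should remove them now". Two further items ask about self-stimulation and invite free-text comments. The 4-week follow-up has no ear-seed item.

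Section 6.2.4 times the first follow-up "at 1 week (+/- 4 days) of patient's ED discharge for both arms", and Section 6.2.5 times the second "at 4 week (+/- 4 days) of patient's ED discharge for both arms". On earlier experience, Section 2.2 reports: "Seven of eight patients reported retaining the ear seeds in place until the 1-week follow-up".

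**The concern.** For a patient still wearing the seeds comfortably when the 1-week form arrives, the two instructions cannot both be followed. The protocol text lets wear continue; the form ends it without condition. Because the prompt appears only on the form, whether a patient receives it depends on whether they answer, and the day it arrives depends on when they answer. Within one arm, a treatment component could then end under different instructions for reasons tied to survey response.

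The form also cannot record the protocol's own default end of wear, which is the seeds falling off. Taken literally, a patient whose seeds fell off did not remove them. That patient would choose the negative answer, be told to remove something no longer there, and be asked for no date.

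At stake is the interpretation of anything measured after the prompt, and the usefulness of the ear-seed data for a later trial. Section 1.1 makes refining procedures the primary objective, and Section 9.5.1 counts data quality and completeness among the feasibility aims. Section 2.1 names the lack of auricular-therapy data beyond two days after discharge as a gap this study will fill.

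**Working it through.** No stated figure needs reproducing. The point rests on comparing texts, followed by an illustrative headcount.

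**1. The instructions side by side**

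| Source | Who receives it | End of wear |
|---|---|---|
| Sections 3 and 5.1 | Acupuncture patients given seeds | When they fall off, or on removal for discomfort; no date |
| 1-week form, Appendix B | Seed recipients who answer the form | On answering, if not yet removed |
| After-care sheet (Section 5.1) | Acupuncture patients | Unknown; text not in the documents |

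The discomfort clause does not resolve the conflict, because the form's prompt is not tied to discomfort.

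**2. Timing.** The first follow-up falls on day 7 − 4 = 3 to day 7 + 4 = 11. The second falls on day 28 − 4 = 24 to day 28 + 4 = 32. The prompt can therefore arrive anywhere in an eight-day span, always before the 4-week assessment.

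**3. Which outcomes come after the prompt.** On the 1-week form, medication is Section 1, pain Section 2, anxiety Section 3, satisfaction Section 4 and ear seeds Section 5. Answered in that order, the 1-week scores are given before the prompt is seen. Post-treatment and ED-discharge scores are earlier still. What follows is 4-week pain and anxiety, and medication use after the prompt; the Section 6.1 table marks all of these as secondary assessments.

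**4. Meaning of the negative answer.** It covers seeds still in place and, read literally, seeds that fell off. What is captured is a date for patients who removed them, plus any free text. What is missing is a dated entry for seeds that fell off, whether the prompt was followed, and everything for patients who do not answer.

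**5. Illustrative headcount.** Inputs:

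- Acupuncture patients: 150/2 = 75 (150 from Section 9.2; equal allocation assumed).
- Share given seeds: 14/19 = 74% (second observational study, Section 2.2) up to 100% (assumed ceiling).
- Share still wearing them at 1 week: 7/8 = 87.5% (same study) as the upper value. The exact 95% confidence interval is 47% to 99.7%, so 50% is assumed as the lower value.
- Share answering the 1-week form: 16/46 = 35% (30-day telephone follow-up in the pilot RCT) to 78% (that pilot's completion rate inside the ED). Neither is a 1-week rate, so both are assumptions.

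Formulas: wearing = 75 × share given seeds × share still wearing; told = wearing × response; not told = wearing × (1 − response).

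- Fewest wearing: 75 × 14/19 × 0.50 = 27.6. Most wearing: 75 × 1.00 × 0.875 = 65.6.
- Fewest told: 27.6 × 16/46 = 9.6. Most told: 65.6 × 0.78 = 51.2.
- Fewest not told: 27.6 × 0.22 = 6.1. Most not told: 65.6 × 30/46 = 42.8.

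So about 28 to 66 patients would still be wearing seeds. About 10 to 51 would be told by the form to remove them, and about 6 to 43 would not. Each range takes its own extreme combination of inputs, so the ends do not pair up across ranges.

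**The case against.** The strongest reply concerns consequences. The wording conflict itself is plain.

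- **The after-care sheet may already give a wear time.** If it states a limit matching the form, responders and non-responders would have had the same advice from the start. This stands: the documents support saying that non-responders *may* lack the removal instruction, and no more. The sheet cannot, however, remove the conflict between Sections 3 and 5.1 and the form.
- **A reader might infer that wear time cannot be derived, or that patients whose seeds fell off are forced into a wrong answer.** Neither follows. The form records removal dates and has a comments field, and some patients may count falling off as removal and enter a date. Capture is partial and ambiguous.
- **A reader might infer that the trial's main results are at risk.** They are not. Section 3 makes recruitment and retention the primary outcomes, the in-ED and discharge scores precede the prompt, Section 9.5 plans descriptive summaries, and no between-arm efficacy test is specified for this trial. Seed exposure also varies by design, since use is at the acupuncturist's discretion.
- **A headcount is not an effect.** The documents do not say how long seeds last beyond 1 week, so the extra wear among patients who are not prompted could be trivial. The retention figure comes from eight patients. This also stands.

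What survives is a contradiction between two current texts about a component of the intervention, and a form that lacks an answer for the expected way wear ends.

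**Conclusion.** The point holds as a minor inconsistency. Sections 3 and 5.1 and the 1-week form give incompatible directions to any patient still comfortably wearing seeds at that follow-up, and one form answer merges seeds still in place with seeds that fell off. Under the stated assumptions, about 10 to 51 of 75 acupuncture patients would receive the conflicting prompt. The width of that range shows how little the documents settle the number.

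The reach is limited to the secondary 4-week pain, anxiety and medication data and to the quality of the ear-seed data. In-ED, discharge, recruitment and retention outcomes are unaffected, and so are the 1-week scores if the form is answered in the order laid out. It may be tempting to conclude that treatment length in the acupuncture arm is determined by survey response. That would require the after-care sheet to be silent or to agree with Section 5.1, patients to follow the prompt, and seeds to last well past 1 week. The documents establish none of these.

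**What to change.** Reconcile Section 3, Section 5.1, the 1-week form and the after-care sheet so that every patient given seeds gets the same end-of-wear instruction at discharge and at follow-up. Which instruction that should be is for the sponsor to decide.

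On the form, replace the yes/no item with three answers: still in place; I removed them (date); they fell off (date). Keep or drop any removal prompt to match the reconciled instruction. The three answers work in either case.

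The cost is a wording change in the affected texts and one extra answer option with a date field in REDCap. Sample size, visits and analyses do not change.
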